## 8.9. PHARMACOKINETIC ANALYSIS OF NICOTINE PLASMA CONCENTRATION

PK parameters of plasma nicotine levels will be calculated using noncompartmental methods with the Phoenix WinNonlin version 8.3 software platform (Certara, Princeton, NJ). Plasma concentrations and the computed plasma PK parameters will be listed for each study product and subject.

The following PK parameters will be calculated; all parameters will be baseline-adjusted using the value at time -5 minutes:

- $C_{max,0-120}$  = Maximum plasma concentration during defined use session
- $T_{max,0-120}$  = Time of maximum plasma concentration during defined use session
- $AUC_{0-120}$  = Area under the plasma concentration-time curve from time 0 to 120 minutes during defined use session
- $C_{avg,0-120}$  = Average concentration from 0 to 120 minutes defined as  $AUC_{0-120}/120$  minutes
- $C_{max,120-180}$  = Maximum plasma concentration during the *ad libitum* puffing session
- $T_{max,120-180}$  = Time of maximum plasma concentration during the *ad libitum* puffing session
- $AUC_{120-180}$  = Area under the plasma concentration-time curve from time 120 minutes to 180 minutes during the *ad libitum* puffing session
- $C_{avg,120-180}$  = Average concentration from 120 to 180 minutes defined as  $AUC_{120-180}/60$  minutes
- $AUC_{0-180}$  = Area under the plasma concentration-time curve from time 0 minutes to 180 minutes during both puffing sessions
- $RC_{max}$  = Ratio of  $C_{max,120-180}/C_{max,0-120}$
- $RC_{avg}$  = Ratio of  $C_{avg,120-180}/C_{avg,0-120}$

A one-way or repeated measures analysis of variance will be conducted on the Outcomes Population  $C_{max,0-120}$  and  $AUC_{0-120}$  to assess for statistical differences between the Usual Brand combustible cigarette and the blu disposable e-cigarettes. Significance based on a Dunnett's multiple comparison assessment will be reported.

Statistical Analysis Plan  
Protocol No.: Fontem-PK-01

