	
• $C_{max,120-180}$ = Maximum plasma concentration during the ad libitum puffing session• $T_{max,120-180}$ = Time of maximum plasma concentration during the ad libitum puffing session• $AUC_{120-180}$ = Area under the plasma concentration-time curve from time 120 minutes to 180 minutes during the ad libitum puffing session• $C_{avg,120-180}$ = Average concentration from 120 to 180 minutes defined as $AUC_{120-180}/60$ minutes.• AUC_{0-180} = Area under the plasma concentration-time curve from time 0 minutes to 180 minutes during both puffing sessions• Ratio of $C_{max,120-180}/C_{max,0-120}$ = ratio of these two parameters• Ratio of $C_{avg,120-180}/C_{avg,0-120}$ = ratio of these two parameters 
A one-way or repeated measures analysis of variance will be conducted on $C_{max,0-120}$ and AUC_{0-120} to assess for statistical differences between the Usual Brand combustible cigarette and the blu disposable e-cigarettes. Significance based on a Dunnett's multiple comparison assessment will be reported.
 
Analysis of Subjective Effects Measures: Where applicable, responses to the questionnaires recorded as Visual Analog Scale (VAS) scores or Likert scales will be treated as continuous variables and summarized descriptively by study product and time point for each questionnaire item using means, standard deviations (SD), medians, and ranges. The maximum response (E_{max}) and time to maximum response (T_{max}) will be determined for the Urge to Smoke questionnaire.
 
Analysis of Puff Topography Data: Summary statistics of the puff topography parameters will be presented including means, SD, medians, and ranges.
 
Analysis of Safety Data: Safety data will be descriptively summarized by study product. Individual data will be provided in listings. AEs and incidence of device events and malfunction/misuse will be tabulated, and summary statistics for vital signs may be computed and provided, as deemed appropriate.

--	--

STUDY EVENTS FLOW CHART

	Screening Visit 1	Product use phase (Visits 2 to 7)	Follow-up phone call/visit
Informed consent	X		
Socio-demographic data	X		
Biochemistry, hematology, and urinalysis	X		
Urine drugs of abuse screen	X		
Urine cotinine level (must be >200 ng/mL)	X		
Alcohol breath test	X		
Inclusion/exclusion criteria	X	X	
Urine pregnancy test ¹	X	X	
Electrocardiogram ²	X		
Prior/concomitant medications	X	X	X
COVID-19 screening ³	X	X	

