1. INTRODUCTION AND BACKGROUND

1.1 Background

Fontem US LLC is undertaking clinical studies to evaluate electronic nicotine delivery systems (ENDS) to provide an alternative to combustible cigarettes for smokers. Upon user inhalation, an e-liquid solution containing nicotine, glycerol, propylene glycol, and flavor agents is heated and delivered into the lungs via an aerosol.

The objective of ENDS products is to provide sufficiently satisfying alternatives to cigarette smoking. According to the National Academies of Sciences, Engineering, and Medicine, “There is conclusive evidence that completely substituting e-cigarettes for combustible tobacco cigarettes reduces users’ exposure to numerous toxicants and carcinogens present in combustible tobacco cigarettes” [1].

Over the past several years, a number of pharmacokinetic (PK)/pharmacodynamic studies of ENDS have been published. Very early devices showed very little, if any, nicotine absorption, compared with the typical 15 ng/mL Cmax achieved almost immediately after smoking a combustible cigarette after 12 hours of abstinence [2, 3]. Through innovation, nicotine delivery has improved, with Cmax after acute use (typically 10 puffs or 5 minutes) following 12 hours of overnight abstinence from smoking or vaping ranging from 25% to near 100% of combustible cigarettes from some devices and e-liquid nicotine concentrations [4-10]. Puff topography parameters, including puff duration, puff volume, and flow rate have also been investigated [11-18].

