10. DATA ANALYSIS

A brief description of the statistical analysis is included below, detailed methodology for all summary and statistical analyses of the data collected in this trial will be documented in a statistical analysis plan (SAP) prepared by LA Clinical Trials, LLC and agreed upon by the sponsor. The SAP may modify the plans outlined in the protocol; however, any major modifications of the primary endpoints and/or their analysis will also be reflected in a protocol amendment. If deemed appropriate, additional statistical analyses other than those described in this section may be performed and included in the SAP.

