### **3.4. STUDY DESIGN**

This will be a part-randomized, open-label abuse liability assessment and puffing topography study of nicotine-containing products carried out in 20 healthy adult volunteers who smoke combustible cigarettes. The schedule of events is presented in Section 10.

Statistical Analysis Plan  
Protocol No.: Fontem-PK-01

After screening, subjects will attend the study site 6 times (Visits 2-7). Prior to each visit, subjects will be required to refrain from using any nicotine-containing products for a period of at least 12 hours before study product use.

During their second visit (Visit 2), the subjects will smoke their usual brand cigarette during 2 use sessions. In the first session, subjects will smoke a single combustible cigarette of their usual brand by taking 10 puffs, 30 seconds apart. Blood samples (5 mL) will be obtained for plasma nicotine analysis at -5, 3, 5, 7, 10, 15, 20, 30, 45, 60, 90, and 120 minutes relative to the first puff on the cigarette. Blood pressure and heart rate will be recorded at -10 (baseline), 8, 60, and 120 minutes. Subjects will be asked to complete several subjective effects questionnaires at various points either before, during, or after product use.

In the second session, which will begin immediately after the 120 minute blood draw and after all questionnaires have been completed, subjects will be allowed to take *ad libitum* puffs on their usual brand cigarette for a period of 60 minutes (1 hour) while puffing topography measurements are made with a CReSS Pocket device. Subjects may use as many cigarettes as they like. Blood samples for nicotine PK analysis will be drawn at 135, 150, 165, and 180 minutes relative to the first puff on the cigarette at the visit (i.e., at 15, 30, 45, and 60 minutes of the *ad lib* session). Blood pressure and heart rate will be recorded at 180 minutes. Subjective effects questionnaires will also be completed at specified time points.

At the end of Visit 2, subjects will be randomized into a product use sequence for testing the investigational products (blu disposable e-cigarettes).

Subjects will then visit the study site on 5 subsequent occasions (Visits 3-7); at each visit, the subjects will use their assigned blu disposable e-cigarette during 2 use sessions (standardized and *ad lib*, same as at Visit 2). Study procedures during the 2 use sessions will be the same as at Visit 2.

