## **4. RANDOMIZATION AND BLINDING**

### **4.1. RANDOMIZATION**

Eligible subjects at Visit 2 will be assigned a randomization number beginning with 2001. The randomization will determine the order in which the subjects will test the study products at Visits 3 to 7. The randomization code for the study products will be produced using a computer-generated Latin-square procedure.

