## **6. SAMPLE SIZE CALCULATION**

Since this study is the first to examine the nicotine PK in subjects using these blu disposable e-cigarettes, no formal power calculations were performed. The sample size is typical of other studies reported in literature examining the PK and subjective effects of different tobacco/nicotine products. A sample size of 20 subjects has been determined adequate to meet the study objectives.

Statistical Analysis Plan  
Protocol No.: Fontem-PK-01

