### **7.2. SUMMARY STATISTICS**

Continuous variables will be summarized using descriptive statistics including number of subjects, mean, median, standard deviation (SD), minimum and maximum values of the raw data, coefficient of variance (CV; PK concentration and PK parameters), geometric mean, and geometric CV (%) (PK parameters only). Means and medians will be reported to one more significant digit than the raw data values being analyzed. Standard deviations will be reported to two more significant digits, and the minimum and maximum will be reported to the same number of significant digits as the raw data values being analyzed.

Categorical variables will be summarized as the number and percentage of subjects per category. All percentages will be rounded to one decimal point. To ensure completeness, all summaries for categorical and discrete variables will include all categories, even if none of the subjects had a response in a particular category. Denominators for each analysis will be based on the population of interest (e.g., Safety Population; subjects with non-missing data) unless otherwise noted.

In general, all data will be listed by subject and time point.

SAS software (version 9.3 or higher, Cary, NC) will be used for data presentation and summarization including summary tables, graphs, and data listings not associated with the nicotine concentration or PK parameters.

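### The one-way ANOVA option for the nicotine comparisons does not fit a six-product within-subject design, can miss real differences, and should give way to one prespecified subject-blocked model that allows unequal product variances

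*SAP*

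**What the plan says.** SAP 8.9 gives the test: "A one-way or repeated measures analysis of variance will be conducted on the Outcomes Population". It applies to Cmax,0-120 and AUC0-120, with Dunnett comparisons against the usual-brand cigarette. Protocol 10.3.1 has the same sentence, and the Statistics part of the synopsis also reads "A one-way or repeated measures analysis of variance will be conducted on". None of the three says when each model would be used, and none states alpha, sidedness, analysis scale or covariance structure.

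The design is within-subject. The usual brand is smoked at Visit 2. At Visits 3 to 7, according to SAP 3.4, "at each visit, the subjects will use their assigned blu disposable e-cigarette during 2 use sessions". SAP 4.1 shows that only the order of the five e-cigarettes is randomized: "The randomization will determine the order in which the subjects will test the study products at Visits 3 to 7". Protocol 5.2 aims for 20 subjects completing all six product-use visits.

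On sample size, SAP 6 says "no formal power calculations were performed". SAP 9 records no changes to the planned analyses, so the choice of model stays open.

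**The concern.** A one-way ANOVA treats the six product groups as different people. Here they are the same people measured six times. Smokers differ in how much nicotine they take up, and a one-way model leaves that difference in the error term, although it cancels from every e-cigarette-minus-cigarette contrast within a subject.

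This is the plan's only inferential method: one test on two parameters, with five comparisons each. Subjective effects, topography, mass change and safety are summarized descriptively. The test serves the first primary objective, in a 20-subject study with no power calculation. A missed difference in nicotine uptake could be taken as similarity to a cigarette.

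**Working it through.** The plan has no power or precision figure to reproduce, so the check compares the two permitted models.

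**Inputs from the documents.** There are 20 subjects and six products, hence 120 values per parameter, and five Dunnett comparisons. Protocol 1.1 describes e-cigarette Cmax as "ranging from 25% to near 100% of combustible cigarettes from some devices and e-liquid nicotine concentrations".

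**Assumptions, because the documents are silent.** Two-sided family-wise alpha is 0.05 per parameter and all 20 subjects complete. Variances and correlations are shown as ranges.

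**1. Standard errors with equal variances.** Let σ² be the total variance and ρ the within-subject correlation.
- Correct SE of a product contrast: √(2σ²(1−ρ)/20)
- SE used by the one-way model: √(2σ²/20)
- Ratio: 1/√(1−ρ), which is 1/√0.7 = 1.20, 1/√0.5 = 1.41 and 1/√0.3 = 1.83 at ρ = 0.3, 0.5 and 0.7

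Error degrees of freedom are 120 − 6 = 114 (one-way) and 19 × 5 = 95 (repeated measures). The two-sided Dunnett critical values are about 2.55 and 2.56, so degrees of freedom hardly matter. The simultaneous interval half-width is 2.547 × √(2/20) = 0.81σ for one-way. For repeated measures it is 2.556 × √(2(1−ρ)/20) = 0.68σ, 0.57σ and 0.44σ at the three correlations.

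**2. False positives with equal variances (simulated, normal data).** One-way family-wise error is 1.2-1.5% at ρ = 0.3, 0.3-0.4% at 0.5 and 0.01-0.03% at 0.7, across repeated runs. Repeated measures stays at about 5%. At ρ = 0 both give 5.0%.

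**3. Power per comparison (simulated).** Value = product ratio × lognormal subject effect × lognormal residual, analysed on the raw scale, true ratio 0.70:

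| Between-subject CV | Within-subject CV | One-way | Repeated measures |
|---|---|---|---|
| 30% | 60% | 24% | 32% |
| 30% | 50% | 33% | 46% |
| 30% | 30% | 67% | 90% |
| 50% | 50% | 18% | 41% |
| 60% | 30% | 18% | 83% |

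The first and last rows are the smallest and largest gaps on the 30-60% grid: 8 and 65 points. The raw-scale correlation is b²/(b² + w² + b²w²), where b and w are the between- and within-subject CVs. It is 0.09/0.4824 = 0.19 in the first row and 0.36/0.4824 = 0.75 in the last.

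By true ratio, the gap is about 3-19 points at 0.85, 8-65 at 0.70, 2-38 at 0.60, at most 5 at 0.40 and about 0 at 0.25. With the five products spread evenly over 0.25 to 1.00, the two models disagree on at least one comparison in 21-69% of simulated trials. With four at 0.40 and one at 0.70 they disagree in 9-43%.

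**4. Unequal product variances.** Both models pool the error over all six products. Suppose the cigarette SD is twice that of each e-cigarette, with ρ = 0. The pooled variance is (5 × 1 + 4)/6 = 1.5, so the contrast variance used is 2 × 1.5/20 = 0.15, while the true one is (1 + 4)/20 = 0.25. The SE is too small by a factor √(0.15/0.25) = 0.77. Simulated family-wise error under no difference is then 13-16% for repeated measures at ρ from 0 to 0.7. For one-way it is 13% at ρ = 0 and about 4% at ρ = 0.5. Paired contrasts with Bonferroni stay at about 3%.

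The lognormal model behaves the same way, because raw-scale variance follows the mean. Put four e-cigarettes at 0.25 and one equal to the cigarette. The average variance is (4 × 0.0625 + 2)/6 = 0.375 of the cigarette's. One-way is then too liberal for the equal product whenever 1 − ρ exceeds 0.375. At between-subject CV 30% and within-subject CV 50%, ρ = 0.09/0.3625 = 0.25, and one-way rejects that true null in 7.4% of trials, against a nominal rate of about 1.2% per comparison. Raw-scale pooled repeated measures rejects it in 2.6-10.4% across the grid. Repeated measures on the log scale rejects it in 1.1-1.4%.

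**The case against.** Repeated measures is already one of the two options, and the wording may be a slip for a one-way repeated measures ANOVA. If so, the harm may never arise, though the same edit settles it. Large differences would be found under either model, and every size above rests on assumed variances. Both points stand.

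Five stronger readings are tempting, and the documents do not support them.
- *Choosing the model after seeing the data inflates false positives.* With normal data and equal variances, taking whichever model is significant gives at most 5.0%.
- *The one-way model is always safe on false positives.* That holds only if product variances are about equal (step 4).
- *The estimates would be biased.* With complete data both models use the same product means; only the error term differs.
- *A reader could not trace a non-significant result to its error term.* SAP 8.9 and Protocol 10.3.1 list PK parameters by subject and product, so paired contrasts can be recomputed, although none is planned for reporting.
- *Deleting the one-way option is enough.* Raw-scale pooled repeated measures can exceed its error rate when variances differ.

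It can also be said that alpha, scale and intervals are separate omissions. They are, but they belong to the sentence that has to be rewritten.

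**Conclusion.** The concern holds as a defect of specification: one of the two permitted models does not fit the design. That follows from the documents alone. Its consequence is conditional. With positive within-subject correlation and equal product variances, the one-way test is conservative. In the lognormal model, whose raw-scale variances follow the product means, it costs about 8 to 65 points of power at a true ratio of 0.70, with 20 completers and both CVs between 30% and 60%. The loss shrinks to almost nothing for products far below the cigarette or with no correlation. With unequal variances, both pooled-error models can reject too often, so the replacement must deal with variance as well as pairing. The plan should be corrected before results are seen. Nothing in the documents shows that the one-way model will in fact be used.

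**What to change.** In SAP 8.9 delete *one-way or* and prespecify one model: a linear mixed model with product (six levels) as fixed effect and subject as random effect or block, using all available visits. SAP 2 gives the SAP's analyses precedence over the protocol's outline, so this edit governs. Align Protocol 10.3.1 and the synopsis with it.

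Choose one error structure now, the same for both parameters:
- the log scale, with a stated rule for baseline-adjusted values at or below zero that does not involve changing scale; or
- the raw scale with product-specific variances, through an unstructured or heterogeneous covariance or comparison-specific paired contrasts with a multiplicity adjustment.

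Do not use raw-scale repeated measures with a pooled error term. State a two-sided family-wise alpha of 0.05 over the five comparisons for each parameter, and report each contrast with its adjusted 95% confidence interval.

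The cost is rewording, with no new data or visits. Protocol 10 says "any major modifications of the primary endpoints and/or their analysis will also be reflected in a protocol amendment", so the sponsor must decide whether this counts as major; repeated measures is already permitted, which argues that it does not. One limit remains: the usual brand is always tested at Visit 2, so no model can separate it from a visit effect.

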2.2 Study Endpoints

Primary endpoints:

- Baseline-adjusted plasma nicotine $C_{max,0-120}$, $C_{avg,0-120}$, $T_{max,0-120}$, AUC_{0-120} , $C_{max,120-180}$, $T_{max,120-180}$, $AUC_{120-180}$, $C_{avg,120-180}$, AUC_{0-180}
- Ratio of $C_{max,120-180}/C_{max,0-120}$
- Ratio of $C_{avg,120-180}/C_{avg,0-120}$
- Subjective effects measures:
 - Product liking assessment
 - Intent to Use Product Again assessment
 - Urge to Smoke Questionnaire
 - Product Evaluation Scale (PES)
- Mass change of blu disposable e-cigarettes during puffing

Secondary endpoints:

- Puff topography (e.g., count, duration, volume, flow rate, and inter-puff interval)

Safety endpoints:

- Heart rate and blood pressure during product use sessions
- Adverse events (AE)/Serious adverse events (SAE)

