10.3.1 Nicotine Pharmacokinetic Analysis

Individual nicotine concentrations will be adjusted for baseline nicotine (“baseline-adjusted”) and all PK parameters will be calculated based on the adjusted concentrations. Baseline adjustment will be performed by subtraction of the baseline nicotine concentration from each nicotine concentration obtained after test product use on that day for each subject.

Pharmacokinetic parameters of plasma nicotine levels will be calculated using noncompartmental methods with the Phoenix WinNonlin version 8 software platform (Certara, Princeton, NJ). Plasma concentrations and the computed plasma PK parameters will be listed for each study product and subject.

Plasma nicotine levels will be plotted as mean concentration in relation to time, with 95% confidence intervals of the mean for each product at each time point.

The following PK parameters will be calculated; all parameters will be baseline-adjusted using the value at time -5 minutes:

- $C_{max,0-120}$ = Maximum plasma concentration during defined use session
- $T_{max,0-120}$ = Time of maximum plasma concentration during defined use session
- AUC_{0-120} = Area under the plasma concentration-time curve from time 0 to 120 minutes during defined use session
- $Cavg_{0-120}$ = Average concentration from 0 to 120 minutes defined as $AUC_{0-120}/120$ minutes.
- $C_{max,120-180}$ = Maximum plasma concentration during the *ad libitum* puffing session
- $T_{max,120-180}$ = Time of maximum plasma concentration during the *ad libitum* puffing session
- $AUC_{120-180}$ = Area under the plasma concentration-time curve from time 120 minutes to 180 minutes during the *ad libitum* puffing session
- $Cavg_{120-180}$ = Average concentration from 120 to 180 minutes defined as $AUC_{120-180}/60$ minutes.
- AUC_{0-180} = Area under the plasma concentration-time curve from time 0 minutes to 180 minutes during both puffing sessions
- Ratio of $C_{max,120-180}/C_{max,0-120}$ = ratio of these two parameters
- Ratio of $Cavg_{120-180}/Cavg_{0-120}$ = ratio of these two parameters

Plasma concentrations below the limit of quantitation will be set to one-half of the lower limit of quantitation for the calculation of descriptive statistics of unadjusted plasma nicotine concentrations and for the calculation of baseline-adjusted nicotine concentrations.

Nicotine concentrations and PK parameters will be listed by subject and summarized by study product using descriptive statistics.

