A one-way or repeated measures analysis of variance will be conducted on the Outcomes Population Cmax₀₋₁₂₀ and AUC₀₋₁₂₀ to assess for statistical differences between the Usual Brand combustible cigarette and the blu disposable e-cigarettes. Significance based on a Dunnett's multiple comparison assessment will be reported.

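### The Cmax,0-120 and AUC0-120 tests name no analysis scale and report significance only, so no e-cigarette/cigarette ratio or confidence interval is planned

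*SAP*

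**What the plan says.** The first primary objective (Protocol 2.1, SAP 3.2.1) is to determine nicotine pharmacokinetics with the e-cigarettes relative to a combustible cigarette.

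The only hypothesis tests on PK data are in SAP 8.9 and, in matching words, Protocol 10.3.1: "A one-way or repeated measures analysis of variance will be conducted on the Outcomes Population" for Cmax,0-120 and AUC0-120, "to assess for statistical differences between the Usual Brand combustible cigarette and the blu disposable e-cigarettes". The stated output is one sentence: "Significance based on a Dunnett's multiple comparison assessment will be reported". Neither document gives a transformation, model terms, significance level or sidedness.

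For description, SAP 7.2 lists arithmetic mean, SD and CV and adds "geometric mean, and geometric CV (%) (PK parameters only". Protocol 10.3.1 plans a plot of mean concentration over time "with 95% confidence intervals of the mean for each product at each time point". Those intervals are for one product at a time. The ratios defined as endpoints divide the ad libitum session by the defined session within a product; they do not compare an e-cigarette with the cigarette.

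Baseline adjustment is by subtraction (SAP 8.9.3), so adjusted values can be zero or negative. No power calculation was made (Protocol 10.1, SAP 6).

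**The concern.** The planned output does not answer the objective. A reader would learn whether each e-cigarette differs significantly from the cigarette, but not by how much or how precisely. With no power calculation, a non-significant result could mean similar uptake or too little information, and nothing in the planned output separates the two. The results are meant to support a regulatory submission (Protocol 1.2), where that distinction matters.

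The scale matters too. The sponsor describes the comparison multiplicatively: Protocol 1.1 gives e-cigarette Cmax in published work as "ranging from 25% to near 100% of combustible cigarettes", and SAP 7.2 uses geometric summaries. If products share a similar CV, a product that delivers half as much has half the SD. A raw-scale analysis of variance pools these spreads into one error term, which then fits neither the cigarette nor the lower-delivery products. Leaving the scale open also allows it to be chosen after the data are seen.

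**Working it through.** There is no planned figure to reproduce: the documents give no SD, CV, power or significance level.

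**Inputs from the documents.** 20 subjects; five e-cigarettes against one cigarette; published Cmax ratios from 25% to near 100%.

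**Assumptions.** Log-normal data; between-subject CV 50%; within-subject CV 40–60%; two-sided 5% family-wise level; complete data; repeated-measures model. Residual df = (20 − 1) × (6 − 1) = 95. The two-sided Dunnett critical value for five comparisons is 2.554.

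**1. What an interval would show (log scale).** σw = √ln(1 + CV²); standard error of a log ratio = σw × √(2/20).
- CV 40%: σw = 0.385, SE = 0.122. Interval factor exp(2.554 × 0.122) = 1.36. Ratio detectable with 80% power: exp(−(2.554 + 0.84) × 0.122) = 0.66.
- CV 60%: σw = 0.555, SE = 0.175. Interval factor 1.56; ratio for 80% power 0.55.

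A true ratio between about 0.6 and 1 would therefore often be non-significant. At a ratio of 0.7, log-scale power per comparison is about 0.65 (CV 40%) or 0.30 (CV 60%), so the result is non-significant about 35% to 70% of the time.

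**2. Why pooling misstates the raw-scale error.** Take visit-level error only, with SD proportional to the mean and all e-cigarettes at ratio r. The true contrast variance is proportional to 1 + r²; the pooled estimate is proportional to 2(1 + 5r²)/6. At r = 0.5 these are 1.25 and 0.75, so the standard error is √(0.75/1.25) = 0.77 of what it should be. At r = 1 both equal 2 and there is no distortion.

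**3. Simulation, 20 subjects, Dunnett on both scales.**

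| All five products at ratio | Simultaneous 95% coverage, raw | Log | Power per comparison, raw / log |
|---|---|---|---|
| 1.0 | 0.95 | 0.95 | – |
| 0.7 | 0.90–0.91 | 0.95 | 0.61 / 0.65 (CV 40%); 0.28 / 0.30 (CV 60%) |
| 0.6 | about 0.88 | 0.95 | – |
| 0.5 | 0.84–0.85 | 0.95 | 0.89 / 0.92 (CV 60%) |

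With products spread at 25/50/70/85/100%, power for the 50% product is 0.71–0.97 raw against 0.92–1.00 log. The product truly equal to the cigarette is flagged 3–4% of the time raw against about 1% log.

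Other assumed CVs (between/within 40/30%, 40/50%, 60/70%) give the same pattern. Raw coverage is 0.84–0.86 with all products at 0.5. With one product equal to the cigarette and four at 0.25, the equal one is flagged 5.2–8.7% of the time raw against 1.2–1.3% log.

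**4. The open model choice.** At ratio 0.75 with CVs 40/30%, raw-scale power per comparison is 69% with repeated measures and 23% with one-way analysis of variance. The type of model can matter more than the scale.

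**5. Non-positive values on the log scale.** Flooring AUC at half the LLOQ × 120 min was checked with an assumed LLOQ of 0.2 ng/mL, cigarette AUC of 600 ng·min/mL, ratio 0.7 and within-subject CV 40%. The floor is 0.5 × 0.2 × 120 = 12, against a typical 0.7 × 600 = 420. On the log scale that lies ln(420/12) = 3.56 below, or 3.56/0.385 = 9.2 within-subject SDs. Flooring 2 of the 100 e-cigarette visits cuts log-scale power from 0.64 to 0.35 and widens the interval factor from 1.36 to 1.62.

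**The case against.** **The raw scale is not stated.** Correct. A reader might infer that the plan prescribes raw-scale testing; the text leaves the scale unspecified. Raw is the default only because no transformation is named.

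**No planned error bar is shown to be wrong.** Also correct, and the tempting stronger reading. The analysis of variance produces no planned interval, and the protocol's plotted intervals are per-product means that do not use its pooled error. The coverage figures describe how well that pooled error measures a contrast, not something the plan will print. Nor can it be said that the SAP drops the plotted intervals: SAP 8.9 does not restate them, but SAP 9 records no changes.

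**The products may be alike.** All five are disposables from one brand at 2.4% nicotine (Protocol 7.1), and the 25–100% range comes from various devices and concentrations. With a common ratio, raw and log power differ by only about 2 to 4 points in the table above. The loss is larger when products differ, and a false-positive rate above 5% for one product needs that product to stand well apart from the others. This limits the cost of a raw-scale test. It does not supply the missing estimate.

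**Ratios can be recovered.** Geometric means by product give a point ratio, and individual parameters are listed, so intervals could be computed later. The objection stands as far as it goes, but such intervals would be post hoc.

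**Nobody says non-significance means similarity.** True; the plan simply gives nothing that would prevent that reading.

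**Log analysis has its own weakness.** This stands and shapes the fix. SAP 8.9.2 anticipates baselines above the 120-minute value, and the test uses the Outcomes Population, which retains those subjects, so non-positive adjusted values are possible.

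**Conclusion.** The point holds in this form: the scale is unspecified, only significance is reported, and no e-cigarette/cigarette difference, ratio or interval is planned for a primary objective that is that comparison. This much rests on the text alone.

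The numerical part is conditional. If spread grows with the mean and the products deliver 50–70% of the cigarette, the pooled raw-scale error corresponds to simultaneous coverage of about 0.84–0.91 rather than 0.95. If all products match the cigarette, it is nominal. These figures depend on assumed CVs, log-normality, complete data and a repeated-measures model, none of which the documents supply.

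The documents do not support the claim that the planned tests are generally invalid. This should be fixed before analysis; it does not undermine the study.

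**What to change.** In SAP 8.9, with matching wording in Protocol 10.3.1:

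- Analyse ln(Cmax,0-120) and ln(AUC0-120) in a within-subject (repeated measures) model with subject and product terms, and delete the one-way option.
- State the family-wise significance level and sidedness.
- Report each e-cigarette/cigarette geometric mean ratio with a Dunnett-adjusted simultaneous 95% confidence interval beside the p-value.
- State that a non-significant result will not be read as similarity.
- Do not floor non-positive baseline-adjusted parameters at half the LLOQ in the primary analysis. List those visits, count them by product, and leave them out of the log-scale model. Apply the same rule to the geometric means in SAP 7.2, which are undefined for such values.
- Add a sensitivity analysis that keeps those visits, such as raw-scale paired differences with confidence intervals or a rank-based comparison. It is needed because omission depends on the outcome and tends to raise the ratio for an affected e-cigarette.

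The cost is about a paragraph of SAP text and a little extra programming, with no new data. A few visits may be lost from the primary model. Protocol Section 10 requires a protocol amendment if this counts as a major change to the analysis of a primary endpoint.
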